Bleeding History					
Bleeding history	Bleeding events in the 12 months prior to index	✓	Baseline	Ongoing	
Description of cohorts based in annualized bleeding rates.
 
See Table 6 for further description of bleed types recorded in the DHR. Derived based on therapy usage recorded in the DHR for suspected, spontaneous, traumatic, or unknown cause of bleeding.

Variable	Description	Captured in DHR	Time period for Analysis	Entry into DHR	Operational notes including Relevant Data Fields in DHR
Treatment History					
Use of prophylaxis	Hemostatic prophylaxis use prior to index	✓	Baseline	Ongoing	Derived based on the therapy usage recorded in the DHR. Inclusion criteria confirmed at time of enrollment based on DHR field confirming that the participant fulfills the AbD inclusion/exclusion criteria.
Prophylaxis type	Medication class utilized for prophylaxis	✓	Baseline	Ongoing	Description of cohorts. Derived based on the therapy usage recorded in the DHR for 'prophylaxis'. Including (but not limited to) description of the use of: FVIII only (any, standard half-life (SHL) products only, extended half-life (EHL) products only, SHL & EHL) Non-factor products only (eg, emicizumab) FVIII and non-factor products
FVIII Consumption	Total FVIII consumption during the 12 months prior to index	✓	Baseline	Ongoing	Description of cohorts. Derived based on reported FVIII consumption for each therapeutic use of FVIII, reported for different prophylaxis types. Will be described based on total FVIII utilized in international units (IUs), as well as IU/kg based on availability of weight data (see note in Table 3).
Infusion Rate	Number of infusions during the 12 months prior to index	✓	Baseline	Ongoing	Description of cohorts. Providing data allows, derived based on the therapy usage and frequency of during individual usage periods recorded in the DHR for any reason. Data is expected to be able to allow for summaries of annualized infusion/injection rate (AIR).

Variable	Description	Captured in DHR	Time period for Analysis	Entry into DHR	Operational notes including Relevant Data Fields in DHR
AAV Status					
AAV Antibody testing	Serostatus for AAV 5 antibodies	✓	Index	At/around time of administration for Roctavian Cohort Ongoing for any testing done during the study	Derived from AAV testing for AAV5 being conducted and result of positive/negative.
Comorbidities					

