Joint bleeds	Bleeds occurring in a joint or target joint	✓	Follow-up	Ongoing	Treated bleeds (see above) regardless of severity, but with a location/localization of 'joint' or 'target joint' in the DHR. Major bleeds will be a sub-set of treated bleeds.

DHR, German Hemophilia Register; FVIII, Coagulation factor VIII

¹ Definition confirmed by DHR as consistent with PedNet. A bleed is classified as severe if the bleed causes pain, swelling, and/or mobility disability and does not end within 24 hours. A bleed is classified as life threatening if the bleed is severe (causes pain, swelling, and/or mobility disability and does not end within 24 hours) and poses a special risk to the patient.

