Variable	Captured in DHR	DHR data field name(s)	Operational definition/description
			
 Presence of known significant hepatic fibrosis or cirrhosis at index is an exclusion criterion, which will be confirmed at time of enrollment based on DHR field confirming that the participant fulfills the AbD inclusion/exclusion criteria.
Other comorbidities	Yes	
 Other diseases 	
 Prespecified list of comorbid diseases including: 
 Malignancy: expected to be defined consistently with the safety outcomes Hypertension is sustained elevation of resting systolic blood pressure (≥ 130 mm Hg), diastolic blood pressure (≥ 80 mm Hg), or both¹⁵ Osteoporosis is a progressive metabolic bone disease that decreases bone mineral density (bone mass per unit volume), with deterioration of bone structure. It is defined as DXA results for T-scores $\leq -2.5$¹⁶
Von Willebrand factor	Yes		
 Measured in IU/mL
Target joints	Yes	
 Localization Bleeding location 	
 Yes/No If localization = "target joint", then target joints will = "yes" Number and location of target joints will be based on location (shoulder, elbow, hip, knee, ankle joint, or other joint) and side (left, right, not applicable, or unknown) of bleeds identified as "target joint" For example, if target joint bleeds are recorded at the same location on both sides (e.g., a target joint bleed at the left ankle and a separate target joint bleed at the right ankle), this will be counted as 2 separate target joints. If the target joint location is "other joint" or the side of bleeding is "not applicable or unknown", the number of target joints identified from the bleed will be counted as 1 target joint.
AAV5 antibody status (ever)	Yes	
 Have you been tested for AAV antibodies? If yes: tested serotype If yes: date If yes: result (positive/negative) 	
 Derived from AAV testing for AAV5 being conducted and result of positive/negative
Prophylaxis type	Yes	
 Preparation/ medicinal product 	
 FVIII only Non-factor products only (e.g., Emicizumab) FVIII and non-factor products See Table 4 for drug classifications

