SoC class switching	Yes (calculated)	
 Occasion Preparation/ medicinal product Therapy start End of therapy Start of reporting period End of reporting period 	
 Participants who switched between SoC treatments during the 12 months prior to index date (SHL to EHL; SHL to emicizumab; EHL to emicizumab [and vice-versa]; PD to emicizumab). Participants will be considered to have a switch if occasion = "prophylaxis" for ≥ 2 different medicinal products identified as SoC treatment classes in Table 4 with therapy dates that do not overlap
Prior ABR (before index date)	Yes (calculated)	
 Occasion Therapy scheme Severity Localization 	
 Using the most recent 12 months of pre-index data (when available), calculate ABR using number of prior bleeds within the reporting period start and stop dates

Variable	Captured in DHR	DHR data field name(s)	Operational definition/description
		
 Start of reporting period End of reporting period 	
 Note: a bleeding event is captured if occasion for therapy is spontaneous bleeding/hemorrhage (regardless of severity) Calculate annualized metric of the number of bleeding events multiplied by an individualized factor based on amount of prior history (e.g., if 26 weeks of history, multiply by 2) ABR will be reported as total ABR, treated ABR (therapy scheme = "on-demand"), major ABR (severity = "severe" or "life-threatening"), life-threatening ABR (severity = "life-threatening"), and joint ABR (localization = "joint") See further details in Table 5 for bleed definitions

Abbreviations: AAV: adeno-associated virus; ABR: annualized bleeding rate; AIR: annualized infusion/injection rate; BMI: body mass index; cm: centimeter; DHR: Deutsches Hämophileregister; DXA: dual-energy X-ray absorptiometry; FVIII: coagulation factor VIII; HA: hemophilia A; HCV: hepatitis C virus; HTC: hemophilia treatment center; ITT: immune tolerant therapy; IU: international units; kg: kilogram; mm HG: millimeter of mercury; SoC: standard of care

Note: Data fields in the DHR are either mandatory to be entered into the registry per DHR practices or will be monitored to ensure completeness of data for analyses, however responses may still be unknown.

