Joint ABR	Yes (calculated)	
 Occasion Localization Date of bleed 	
 Number of joint bleeding events per year Calculate ABR using number of bleed events within the relevant time period (≥ 1 year of follow-up, ≥ 2 years of follow-up, ≥ 3 years of follow-up, all available follow-up) Joint bleeds are defined as treated bleeds (see definition above) and based on localization of bleed 
 Note: a bleeding event is captured if occasion for therapy is spontaneous bleeding/hemorrhage (regardless of severity) Calculate annualized metric of the number of bleeding events by dividing the number of bleeds by the number of days in the relevant time period, multiplied by 365.25 	
 ≥ 1 year ≥ 2 years ≥ 3 years All available follow-up
% Zero treated bleeds	Yes (calculated)	
 Therapy scheme Occasion Start of reporting period End of reporting period 	
 % Of participants with zero treated bleeds calculated based on treated bleeding No bleeding events captured within the reporting period start and stop dates The number of participants within the Cohort with zero treated bleeds is divided by the total number of participants in the Cohort See definition for treated bleed above to be used to derive this variable 	
 ≥ 1 year ≥ 2 years ≥ 3 years All available follow-up
% Zero major bleeds	Yes (calculated)	
 Occasion Severity Start of reporting period End of reporting period 	
 % Of participants with zero major bleeds calculated based on major bleeding No bleeding events captured within the reporting period start and stop dates The number of participants within the Cohort with zero major bleeds is divided by the total number of participants in the Cohort See definition for major bleed above to be used to derive this variable 	
 ≥ 1 year ≥ 2 years ≥ 3 years All available follow-up

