Variable	Found by literature review	From previous PS work	Clinical expert opinion	Considerations
Baseline/prior bleeding history (e.g., ABR)	✓	✓	✓	Include regardless of statistical association, based on clinical relevance
Baseline FVIII utilization	✓	✓	✓	Include based on statistical association and correlation with other variables (e.g., baseline/prior bleeding history and baseline prophylaxis class)
Baseline prophylaxis class (FVIII vs. emicizumab)	✓	✓	✓	Include based on statistical association and correlation with other variables (e.g., baseline/prior bleeding history and FVIII utilization)
Age	✓	✓	✓	Include based on statistical association
Height, Weight and/or BMI	✓	✓	✓	Include based on statistical association
Baseline von Willebrand factor (IU/mL)	✓	X	✓	Include based on statistical association
Number of target joints	✓	✓	X	To be considered depending on statistical association and correlation with other variables (e.g., baseline/prior bleeding history and joint health score)
Joint health (e.g., baseline/prior HJHS)	X	X	✓	To be considered depending on statistical association and correlation with other variables (e.g., baseline/prior bleeding history and number of target joints)
Baseline/prior type of bleeds	X	X	✓	To be considered depending on statistical association and correlation with other variables (e.g., baseline/prior bleeding history and target joints)
Geography (HTC/site/region/country)	✓	✓	X	Site to be considered depending on statistical association and correlation with other variables
Prophylaxis class switching (e.g., SHL/PD to EHL/emicizumab)	✓	✓	X	To be considered depending on statistical association and correlation with other variables
Baseline/prior pain (e.g., BPI-sf)	X	X	✓	To be considered depending on statistical association and correlation with other variables (e.g., target joints and HJHS)

Variable	Found by literature review	From previous PS work	Clinical expert opinion	Considerations
Baseline/prior QoL (e.g., haemo-QoL-A)	X	X	✓	To be considered depending on statistical association and correlation with other variables
Activity status	X	X	✓	Not considered as this there is no validated questionnaire for lifestyle factors in PwSHA
Baseline/prior history of liver fibrosis/cirrhosis	✓	X	X	Significant liver fibrosis/cirrhosis is accounted for by the exclusion criteria, but less severe liver fibrosis to be considered based on statistical association

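### The SAP's baseline joint bleeding rate counts only bleeds coded 'joint' and omits those coded 'target joint', which Protocol Table 6 counts as joint bleeds

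*Protocol*

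**What the plan says.** The Prior ABR row of SAP Table 3 (section 7.4.1) lists how each baseline bleeding rate is filtered. For joint bleeds it says "and joint ABR (localization = 'joint" and names no other value. It then adds a pointer: "See further details in Table 5 for bleed definitions".

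The Target joints row of the same table uses a different value of the same field: "If localization = 'target joint', then target joints will = 'yes".

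The Joint ABR row of SAP Table 5 (section 7.4.3), where the pointer leads, says "Joint bleeds are defined as treated bleeds (see definition above) and based on localization of bleed". It does not say which localization values qualify.

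Protocol Table 6 (section 7.2.5.1) does. It describes joint bleeds as "Bleeds occurring in a joint or target joint" and gives the operational rule as treated bleeds of any severity, "but with a location/localization of 'joint' or 'target joint' in the DHR". The protocol's own baseline bleeding-history row (Table 4, section 7.2.3) sends the reader there: "See Table 6 for further description of bleed types recorded in the DHR".

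The candidate propensity-score variables in SAP Table 6 (section 7.8.2.1) include "Baseline/prior type of bleeds".

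**The concern.** The protocol defines a joint bleed by two registry values and applies that definition to baseline through its cross-reference. The SAP's explicit baseline code uses only one of them. A programmer who follows SAP Table 3 literally will drop target-joint bleeds from the baseline joint rate.

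Two uses of that rate are at stake. It has its own row in the baseline clinical characteristics shell (SAP section 12.1, Table 3), with a p-value and standardized difference before and after weighting. It is also a natural way to build the type-of-bleeds candidate for the propensity score, although the SAP does not say that it will be built that way. Under SAP section 7.8.2.3 a remaining standardized difference above 0.25 leads to refinement of the propensity model. Under section 7.9.4.1 covariates still imbalanced enter the model for the joint bleeding rate. A wrongly measured row can therefore prompt a needless correction or fail to prompt a needed one.

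**Working it through.** There is no stated figure to reproduce. The check is a comparison of definitions, followed by simple arithmetic on what the narrower rule does.

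**Definitions side by side**

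| Place | Values counted as a joint bleed |
|---|---|
| Protocol Table 6, joint bleeds | 'joint' or 'target joint' |
| Protocol Table 4, baseline bleeding history | refers to Protocol Table 6 |
| SAP Table 3, Prior ABR | 'joint' |
| SAP Table 5, Joint ABR | none listed |

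**Is the single value only shorthand?** The same bullet in SAP Table 3 defines the major bleeding rate with two severity values, severe and life-threatening. The authors list several values where several apply, so the literal reading of the joint entry is one value.

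**Are the two values distinct?** The Target joints row sets its indicator from 'target joint' in the Localization field, and Protocol Table 6 joins the two labels with 'or'. Both suggest separate values. The registry codebook is not shown, so I take it as an assumption that a bleed carries one value or the other.

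**Effect on one man.** Let s be the share of his joint bleeds coded target joint. Then

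counted rate = true rate × (1 − s).

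With 4 spontaneous joint bleeds in a full 12-month baseline:

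- s = 0: 4 × 1 = 4
- s = 0.25: 4 × 0.75 = 3
- s = 0.5: 4 × 0.5 = 2
- s = 0.75: 4 × 0.25 = 1
- s = 1: 4 × 0 = 0

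The two-value rule gives 4 in every case. In the last case the baseline table would show target joints present beside a joint bleeding rate of zero.

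**Effect on a comparison of cohorts.** The documents give no value of s. Take 60% in one cohort and 20% in the other, purely as assumptions.

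- False imbalance: equal true rates of 2.0 appear as 2.0 × 0.4 = 0.8 and 2.0 × 0.8 = 1.6.
- Hidden imbalance: true rates of 4.0 and 2.0 appear as 4.0 × 0.4 = 1.6 and 2.0 × 0.8 = 1.6.

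Both errors need the share to differ between cohorts. With the same share in both, the ratio of the two rates is preserved and only the level is too low.

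**The case against.** The strongest reply concedes the mismatch but holds that little follows from it.

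- **The forced covariate.** The only bleeding variable that must enter the propensity score is prior ABR (SAP section 7.8.2.1). Total and treated prior ABR carry no localization filter, so target-joint bleeds count in full if either is used. This stands.
- **Other rows.** Presence and number of target joints are reported separately with their own balance statistics. Number of target joints and the joint health score are propensity-score candidates. This stands in part: a cohort difference in target joints would show there, but those rows do not measure how often the joints bleed.
- **Descriptive status.** SAP section 7.8.2.3 puts the focus on variables in the propensity model. If type of bleeds is not selected, the joint row is mainly descriptive. This stands and limits the consequence.
- **A rule already set.** Protocol Table 6 has the fuller definition, so this is a drafting inconsistency. That is fair, but the SAP states the narrower code explicitly and nothing in the SAP overrides it.

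A reader might infer more than the documents support:

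- *That the men with the worst joints are the most understated.* Protocol Table 4 leaves the target-joint label to the recording physician and says it need not follow the ISTH definition. The documents do not tie the code to joint severity.
- *That the cohorts will look balanced when they are not.* The error can run either way, and nothing in the documents shows which is likelier.
- *That a comparison of baseline with follow-up joint bleeding is spoiled.* No change-from-baseline analysis of joint ABR is planned; joint ABR is compared between cohorts during follow-up.

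**Conclusion.** The point holds as a definitional error with limited reach. SAP Table 3 codes the baseline joint bleeding rate more narrowly than Protocol Table 6, and the pointer to SAP Table 5 does not repair it. If the two registry values are mutually exclusive, every bleed coded target joint is lost from that rate.

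The affected items are the baseline joint ABR balance row and, only if it is built from that rate, the type-of-bleeds candidate for the propensity score. The loss equals the share of joint bleeds coded target joint, which could lie anywhere from 0% to 100%; the documents give no figure, so no expected bias can be stated. The primary endpoint, the total and treated prior bleeding rates, and the separate target-joint rows are unaffected.

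**What to change.** In the Prior ABR row of SAP Table 3, code the baseline joint rate as localization in ('joint', 'target joint'). Write the same two values into the Joint ABR row of SAP Table 5, so that baseline and follow-up both match Protocol Table 6 and the narrow code is not the only explicit one in the SAP.

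The cost is one added code value in Table 3 and one clarifying line in Table 5. The Localization field is already used for the target-joint variable, so no new data are needed.

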7.4.2. Exposure Variables

Once inclusion and exclusion criteria are applied to the study population, Table 4 will be used to identify index medications for the Roctavian and SoC Cohorts. This table identifies all drug names as well as the frequency and dosage within each treatment group. Dosages are participant dependent, calculated based on the participant's weight (see Table 3 for weight variable details). Note, the index medication will be Roctavian administration for the Roctavian Cohort and the prophylaxis administration closest to and before the study consent for the SoC Cohort.

To account for any potential concerns regarding heterogeneity of SoC treatments, a sensitivity analysis is planned to analyze the SoC treatment types separately, as outlined in Section 7.9.5.

Treatment patterns, switching between SoC treatment classes (SHL, EHL, PD, and emicizumab), and switching between FVIII alone and FVIII and emicizumab during the study follow-up will be examined in the SoC Cohort as a sensitivity analysis. If treatment switching between SoC classes is observed in >30% of the SoC Cohort, participant characteristics and the primary outcome will be compared between participants who switched SoC treatment versus not to see if there are significant differences between these two SoC sub-Cohorts (standardized mean difference (SMD) > 0.25 or clinically significant after reviewed by clinical experts). If significant differences of outcome between these two SoC sub-Cohorts is detected, separate comparisons will be conducted between Roctavian Cohort and two SoC sub-Cohorts for all outcomes.

As noted in Section 7.3.3, participants in the SoC Cohort who are administered Roctavian after study consent will be removed from the analytic dataset.

Table 4: HA Treatments*

Treatment Type	Treatment Class	Treatment Name	Recommended Treatment Frequency and/or Dose
SoC	Emicizumab	Emicizumab (Hemlibra)	3 mg/kg once every week for the first 4 weeks; Then, 1.5 mg/kg once every week, 3 mg/kg every 2 weeks, or 6 mg/kg every 4 weeks
	SHL products	Kovaltry (Octocog alfa)	20-40 IU/kg administered 2-3 times weekly
		Lonoctocog alfa (Afstyla)	20-50 IU/kg administered 2-3 times weekly
		Octocog alfa (Advate)	20-40 IU/kg every 2-3 days
		Moroctocog alfa (ReFacto)	20-40 IU/kg at intervals of 2-3 days
		Simoctocog alfa (Nuwiq)	20-40 IU/kg at intervals of 2-3 days
		Turoctocog alfa (NovoEight)	20-40 IU/kg administered every second day or 20-50 IU/kg administered 3 times weekly
	EHL products	Damoctocog alfa pegol (Jivi)	45-60 IU/kg every 5 days; Based on clinical characteristics, dose can also be 60 IU/kg every 7 days or 30-40 IU/kg 2 times per week; Maximum dose per injection for prophylaxis should not be higher than approximately 6000 IU

Treatment Type	Treatment Class	Treatment Name	Recommended Treatment Frequency and/or Dose
		Efmoroctocog alfa (Elocta)	50 IU/kg every 3-5 days; Dose may be adjusted to 25-65 IU/kg based on response
		Rurioctocog alfa pegol (Adynovi)	40-50 IU/kg twice weekly in 3-4-day intervals
		Turoctocog alfa pegol (Esperoct)	50 IU/kg every 4 days
	PD products	Voncento	20-40 IU/kg at intervals of 2-3 days
		Beriate	20-40 IU/kg at intervals of 2-3 days
		Octanate	20-40 IU/kg at intervals of 2-3 days
		Haemoctin	20-40 IU/kg at intervals of 2-3 days
		Faktor VIII SDH – Intersero	20-40 IU/kg at intervals of 2-3 days
		Haemate P	One IU of FVIII activity per kg body weight increases the circulating FVIII level by approximately 2.0 IU/dL. Individualize dosage based on weight, type and severity of hemorrhage, FVIII level, and presence of inhibitors.
Roctavian	N/A	Valoctocogene roxaparvovec (Roctavian)	6×10^{13} vg/kg body weight, administered as a single intravenous infusion

Abbreviations: EHL: extended half-life; IU: international units; kg: kilogram; mg: milligram; N/A: not applicable; PD: plasma-derived; SHL: standard half-life; SoC: standard of care; vg: vector genomes

*Note: During the analysis phase, the final list of SoC treatments are expected to be confirmed based on the participants enrolled in the study and their observed data; the final list will be updated for the final study report as necessary.

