7.6. Study Sample Size

The primary goal of HA treatment is to reduce the bleeding rate or to achieve freedom from bleeding. As an approximation of the appropriate number of cases for the data collection accompanying the application, the Institute for Quality and Efficiency in Health Care (IQWiG) conducted the sample size calculation based on ABR for treated bleeds. Evaluation of the ABR is performed using a negative binomial model.

The formula for The sample size calculation is as follows:

$$N_1 \geq \frac{(z_\alpha \sqrt{V_0} + z_\beta \sqrt{V_1})^2}{(\log(R_0) - \log(\lambda_2/\lambda_1))^2}$$

$$N_2 = \theta N_1$$

Where:

$$V_1 = \frac{1}{\mu_t} \left(\frac{1}{\lambda_1} + \frac{1}{\theta \lambda_2} \right) + \frac{(1 + \theta)\varphi}{\theta}$$

V_0 is computed using the fixed marginal total method, the 2nd method recommended by Zhu et al.:²⁷

$$V_{02} = \frac{(1 + R_0\theta)^2}{\mu_t R_0 \theta (\lambda_1 + \theta \lambda_2)} + \frac{(1 + \theta)\varphi}{\theta}$$

N_1 is the sample size for control, N_2 is the sample size for intervention. $\theta = \frac{N_2}{N_1}$, which is the sample size ratio; R_0 is the superiority margin ratio at the null hypothesis. In this case, R_0 is <1 since higher rates are worse. λ_1 is the event rate in the control group, and λ_2 is the event rate in the intervention group. φ is the dispersion parameter, and μ_t is the average exposure time. z_α is the z-score at the significance level, z_β is the z-score at the power value.

When higher rates are worse, the superiority by a margin test hypotheses are

$$H_0: \frac{\lambda_2}{\lambda_1} \geq R_0 \quad \text{vs.} \quad H_1: \frac{\lambda_2}{\lambda_1} < R_0$$

Where $R_0 < 1$.

The relative effect measure is the incidence rate ratio of Roctavian over SoC, which can be tested against the shifted null hypothesis of 0.5, assuming a significance level $\alpha = 2.5\%$ with a one-sided test, and power of at least 80%. Higher values for the ABR (parameter λ) stand for a worse outcome. Furthermore, a distribution of the Sample Roctavian vs. SoC of 1:5 is assumed (sample size ratio $\theta = 0.2$). Other required parameters are the Average Exposure Time ($u_t = 1$ year), the ABR for the SoC and Roctavian groups ($\lambda_{SoC} = 3$, $\lambda_{Roctavian} = 0.85$) and a value for the overdispersion ($\phi = 1.5$). This results in a total sample size of at least 397 participants (Roctavian Cohort $n = 67$, control Cohort $n = 330$).

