7.9.5. Other Analyses

Per the resolution requiring the Routine Data Collection and Evaluations for Valoctocogene Roxaparvovec,⁶⁰ additional analyses comparing outcomes between the Roctavian Cohort and classes of SoC prophylaxis (FVIII products and emicizumab), age groups, as well as for the SoC Cohort AAV 5 antibody status will be evaluated (note that PwSHA treated with Roctavian will be AAV5 negative per the indication for use in Europe).

The feasibility of conducting comparative analyses for subgroups will be described during the 18-month interim report, though analyses are planned *a priori*. As the therapeutic treatment strategy for an individual who consents to this study is made independently of the decision to participate in the study, the sample size of specific sub-Cohorts by SoC therapeutic classes is not known. The feasibility of conducting a comparative analysis will be based on the characteristics of the sub-Cohort, which will impact the ability of the PS to address confounding, as well as sample size. Similarly, the use of AAV antibody testing among PwSHA who are not considering gene therapy is not known currently. AAV antibody status is not known to impact clinical outcomes among PwSHA and therefore is not part of routine clinical practice currently. The feasibility of a comparison to AAV 5 negative among those in the SoC Cohort will be evaluated similarly to the SoC therapeutic classes (based on both characteristics and sample size). Feasibility of analyses will also consider the ability to conduct comparisons for all vs specific objectives (e.g., it may be possible to conduct sub-group analyses for the primary objective, but not for secondary objectives due to missing data). It is assumed *a priori* that analyses will be feasible.

Baseline characteristics and all primary and secondary outcomes (as appropriate) will be reported (using the same analytic methods as described above) for the following analyses:

SoC Cohort Prophylaxis Treatment Type Subgroup Analysis

- Participants within the SoC Cohort will be stratified based on the prophylaxis treatment received at study consent: emicizumab (alone or in combination with another prophylaxis product), SHL products, EHL products, or PD products. See Table 4 for products that fall within each product type.
- Note, the treatment a participant receives at study consent will only be captured in this analysis, any treatment switch after consent will not be captured by this analysis.

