- Each prophylaxis-specific subgroup will be described and compared to the Roctavian Cohort separately as sample size permits.

- A likelihood ratio test will be applied to examine if the SoC treatment types are statistically significantly different.

Age Group Subgroup Analysis

- Participants in both Roctavian and SoC Cohorts will be stratified on age at index date in the following groupings: 18-40, 41-64, 65+.
- A likelihood ratio test will be applied to examine if age groups are statistically significant different across the primary and secondary objective results.

AAV5 Antibody Status Subgroup Analysis

- The study results will be stratified by participants with known AAV5 antibody status at study consent (presence) versus those with no known AAV5 antibody status (absence).
- Missing AAV5 status will be categorized as absence. See Table 3 for operationalization of the AAV5 variable.
- Note, the ability to conduct this subgroup analysis is dependent upon the availability of the AAV5 testing in clinical practice among the SOC cohort.

SoC Switching Sensitivity Analysis

- The study results will be reported for participants in the SoC Cohort who receive Roctavian during the follow-up period and are censored at the time of switching.

Traumatic Bleeds Sensitivity Analysis

If >10% of the population experiences traumatic bleeds as indicated in the DHR (occasion = “traumatic hemorrhage”), a sensitivity analysis will be conducted to compare the ABRs of those with traumatic bleeds as compared to the overall Cohorts (occasion = “spontaneous hemorrhage”).

Switching Sensitivity Analyses

If >15% of the SoC Cohort switches classes of treatment (SHL, EHL, PD, emicizumab) during the follow-up period or if a specific class switching pattern occurs in >10% of the population, a sensitivity analysis will be conducted of participants who remain on the same class for the duration of the follow-up period. ABRs will be calculated for this population that do not switch FVIII classes to understand how this differs from the ABRs for the overall SoC Cohort.

COA measures (as described in Section 7.9.4.4) will be described for participants in the SoC Cohort who stay on the same class of treatment throughout the duration of the follow-up period.

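### If triggered, the SAP 7.4.2 switching rule compares Roctavian with SoC groups defined after index and gated on outcome, so these sensitivity comparisons can reflect selection

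*Protocol*

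**What the plan says.** SAP Section 7.4.2 examines changes between SoC classes (SHL, EHL, PD, emicizumab) during follow-up and calls this a sensitivity analysis. It has two steps.

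- If more than 30% of the SoC Cohort switches class, baseline characteristics and the primary outcome are compared between switchers and non-switchers. A difference counts if the SMD exceeds 0.25 or clinical experts judge it important.
- If the outcome differs, "separate comparisons will be conducted between Roctavian Cohort and two SoC sub-Cohorts for all outcomes".

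The section gives no landmark, no time-varying exposure, no censoring at the class switch and no refitting of the propensity score for the split.

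Two related analyses are in SAP Section 7.9.5. Under different triggers (more than 15% switching, or more than 10% with one specific pattern), "a sensitivity analysis will be conducted of participants who remain on the same class for the duration of the follow-up period". Its stated purpose is to see how their ABRs differ from those of the overall SoC Cohort. Separately, the class subgroup analysis has SoC participants "stratified based on the prophylaxis treatment received at study consent" and ignores later switches. The primary analysis in SAP Section 7.9.3 keeps the SoC Cohort pooled.

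**The concern.** Membership of either sub-Cohort is known only once follow-up has run, while the Roctavian Cohort undergoes no corresponding selection. If people who bleed more are more likely to change product, switchers are enriched for frequent bleeders and non-switchers for people who bleed little. The second condition adds to the problem: the split is carried into comparisons with Roctavian only when the two groups already differ in outcome. Bleeding-driven switching produces that difference even if no SoC class is better than another.

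At stake is how SoC heterogeneity is read. Two ratios for all outcomes, one on each side of the pooled estimate, could be taken as evidence about SoC product classes when they describe who switches.

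**Working it through.** **Inputs from SAP Section 7.6.** SoC ABR 3, Roctavian ABR 0.85, dispersion 1.5, R0 = 0.5, θ = 0.2, one year of exposure, one-sided α 0.025, power 80%. Follow-up of 3 years is from Section 7.3.3.

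**The plan's own figure.**
- V1 = 1/3 + 1/(0.2 × 0.85) + 1.2 × 1.5/0.2 = 15.216.
- V0 = 1.1²/(0.5 × 0.2 × 3.17) + 9 = 12.817.
- N1 = (1.960 × √12.817 + 0.842 × √15.216)² / (ln 0.5 − ln 0.2833)² = 328.84, so 329. N2 = 65.77, so 66.
- The total is 395 against the stated 397 (330 + 67). Power at 330/67 is 80.6%.

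The inputs are therefore read as the plan intends. The true rate ratio is 0.85/3 = 0.283.

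**Illustration 1: switching depends on the individual's underlying rate.** The documents do not say why people switch, so this part is assumed. Individual rates are gamma with mean 3 and shape 1/1.5 (scale 4.5). The yearly switching hazard is 0.03 + b × rate, and switching has no effect on bleeding. Over 3 years:
- share not switching = e^(−0.09) × (1 + 13.5b)^(−2/3)
- ABR in non-switchers = 3/(1 + 13.5b)
- ABR in switchers = (3 − share not switching × ABR in non-switchers) / share switching

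| b | Switch | ABR switchers | ABR non-switchers | Ratio vs switchers | Ratio vs non-switchers |
|---|---|---|---|---|---|
| 0.04 | 31% | 5.29 | 3/1.54 = 1.95 | 0.16 | 0.44 |
| 0.06 | 38% | 5.15 | 3/1.81 = 1.66 | 0.17 | 0.51 |

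At b = 0.02 only 22% switch, so the 30% condition fails and the split would not run. At b = 0.04 the SMD on observed ABR is about 0.85, well above 0.25.

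**Illustration 2: switching depends on recent bleeds.** 400,000 SoC participants were simulated with the same rates and no class effect. Switching was possible after year 1 or year 2, with the odds rising per bleed in that year, and was calibrated to 31%.

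| Odds ratio per bleed | ABR switchers / non-switchers | SMD | Ratio vs switchers / non-switchers |
|---|---|---|---|
| 1.0 | 3.00 / 3.00 | 0.00 | 0.283 / 0.283 |
| 1.1 | 4.10 / 2.51 | 0.39 | 0.207 / 0.339 |
| 1.2 | 4.98 / 2.11 | 0.70 | 0.171 / 0.403 |
| 1.5 | 6.13 / 1.60 | 1.19 | 0.139 / 0.532 |

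The pooled ratio stays at 0.283 in every row. A 10% rise in the odds per bleed is enough to pass the 0.25 condition.

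**Effect of weighting.** These ratios are unweighted. Prior 12-month ABR is always in the propensity score (SAP Section 7.8.2.1). Illustration 1 was repeated with a 12-month baseline count for each person and the score refitted on that count within each sub-comparison. The ratios become about 0.26 and 0.31 at b = 0.04, and about 0.26 and 0.33 at b = 0.06. This assumes a stable individual rate, a complete baseline year, a score well specified in the count and no weight truncation. If whole-cohort weights were kept instead, and the two cohorts had the same baseline distribution as assumed here, the weights would be constant within cohort and the unweighted ratios would stand.

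**Effect of censoring at the switch.** In illustration 1, keeping every SoC participant and censoring at first class switch gives an unadjusted negative binomial ratio of 0.30 to 0.31 against 0.283.

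**The case against.** The strongest reply is that little may follow from this rule. It needs two conditions, it is labelled a sensitivity analysis, p-values for secondary outcomes are nominal (SAP Section 7.9), and a class analysis fixed at consent already exists. Baseline ABR is forced into the score, and where selection acts through a stable bleeding tendency, refitted weights remove most of the distortion. Nothing in the documents says that bleeding drives switching. The background sections stress treatment burden, so convenience is as plausible a reason. All of this stands and limits the size of the point. It does not remove it, because Section 7.4.2 does not say that the score is refitted, and some bias remains when it is.

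A reader might infer four stronger things that the documents do not support.

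- *That the study's main result is biased.* Section 7.9.3 pools the SoC Cohort, and its estimate is untouched.
- *That the same-class analysis in Section 7.9.5 makes the same error against Roctavian.* Its wording is a contrast within SoC, although the general lead-in to that section leaves some ambiguity.
- *That the direction of bias holds whatever the class effect.* It does not. If 31% switch for convenience to a class that halves bleeding, switchers have an ABR of 2.2 and non-switchers 3.0, and the ratios reverse in order (0.85/2.2 = 0.39 against 0.85/3.0 = 0.28).
- *That selection would push the non-switcher ratio past the 0.5 margin.* That appears only in the unweighted figures at the stronger assumed dependence (0.51 and 0.532).

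**Conclusion.** The point holds for the conditional comparisons in Section 7.4.2 and for nothing wider. They divide the comparator on a post-index event, proceed only after an outcome difference is seen, and are then applied to all outcomes. If switching depends on bleeding and the classes are equally effective, the ratio is too low against switchers and too high against non-switchers. Around a true 0.283, illustration 1 gives 0.16 to 0.17 and 0.44 to 0.51 unweighted, or about 0.26 and 0.31 to 0.33 with refitted weights. With switching unrelated to bleeding and no class effect, the bleeding ratio is not distorted. The sizes rest on assumed switching models; the structure of the rule does not. A sensitivity analysis that can move in either direction for reasons unrelated to treatment does not test robustness, and a sounder alternative is already in the plan.

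**What to change.** 1. Remove from SAP Section 7.4.2 the outcome-gated comparisons of Roctavian with switchers and with non-switchers.
2. Base inferential comparisons on SoC heterogeneity on class at consent, as already planned in Section 7.9.5.
3. Keep switching patterns and the same-class ABRs in Section 7.9.5 as descriptive SoC results, and state that they are not compared with Roctavian.
4. If a switching sensitivity analysis against Roctavian is wanted, keep every SoC participant, count bleeds and person-time to the first class switch, censor there, and use the weighted negative binomial model with baseline ABR in the weights.
5. Reconcile the 30% trigger in Section 7.4.2 with the 15% and 10% triggers in Section 7.9.5.

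The cost is SAP wording and one derived censoring date. The downside is less SoC person-time in that analysis and some residual informative censoring (about 0.30 to 0.31 against 0.283, unadjusted, in the same illustration), which the report should state. Protocol Section 10.3 has the SAP finalized before the data cut for the 18-month interim analysis, so the change belongs before then.
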